11.5 Pain Diary Processing

Manual of Operating Procedures

Completed pain diaries will be reviewed for missing data and accuracy (missing dates, ID number) and then brought to the SCC storage facility for processing. Diaries will be stored securely with other CRF's.

11.6 Financial Incentives

Once data collection is complete, the SRC will give the patient their financial incentives based on the number of diaries properly filled out as indicated by table 1.

11.7 Discharge and follow up arrangements

After completion of data collection, the participant will be informed that their participation in the study is complete. At this point the participant will be released and any other medical care will resume.

12.0 Procedures for loss of study medication

Participants will be given contact information for the SRC and [name] at entry into the study.

In the event that a participant loses their study medication they will be instructed to contact the SRC. Loss of study medication may also be identified at follow up phone calls. In this event, the SRC will instruct RC2 to determine which treatment arm the participant is in, obtain an additional inhaler and arrange to give the participant a replacement inhaler. RC2 will record on CRF 11 the date of replacement, and the estimated number of doses used before the initial inhaler was lost.

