2.3 Statistical coordinating center (SCC)

Collection and analysis of data generated for the IMPROVE trial will be coordinated by the PI and research coordinators (RCs) and will leverage the resources of the biostatistics,

epidemiology, and research design (BERD) program at ISMMS to monitor data collection. Responsibilities of the SCC will include:

- **Preparation of study documents**

SCC staff will develop: Protocol, Manual of Operating Procedures (MOP), case report forms (CRFs), and QxQs (question by question), which give the details on answering the questions on every CRF). Materials given to participants (brochure/copy of consent form) will not mention the study acronym “IMPROVE” to avoid suggestive influence of the title.

- **Statistical design and sample size**

SCC statisticians developed the statistical design for the study, including the primary outcome, sample size, randomization strategy, primary analysis strategy, and the complete analysis plan.

- **Training site personnel**

SCC staff has have trained site personnel in all aspects of the study related to: details of the study protocol, data collection procedures, screening and randomization procedures, submitting forms to the SCC, laboratory preparation procedures, and responding to queries from the SCC. SCC staff will also monitor each site to assure that the site coordinators have completed the required training.

- **Receipt and processing of study forms at the SCC**

SCC staff have designed and implemented the data management system for the study, including: electronic data entry, comprehensive editing of the data and preparation of protocol adherence aids, and data extraction for analyses related to research objectives. Data are submitted to the SCC through REDCap, a web-based data entry system. All hardcopy CRF's are maintained in a locked cabinet in a locked room. Once hardcopy enters this **storage facility**, it does not leave. Data are comprehensively edited once received at the SCC, prior to insertion into the main study database. Edit queries are resolved within a few days with the PI. The PI electronically signs off on all case report forms in REDCap before they are finalized. SCC staff also enforces patient confidentiality and privacy rules so that PHI data are not shared inappropriately and so that data are protected by multiple layers of security.

- **Monitoring study progress and data quality**

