5.3.4 Randomization and Enrollment

5.3.4.1 Overview

Individuals who meet inclusion/exclusion criteria will then be consented and randomized. The enrollment procedure is designed to maintain blinding of the participant, the PI and the senior RC. One RC will be unblinded (RC2) for purposes of introducing the study medication, training in proper use of the medication and refilling medication if the participant loses their medication.

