5.3.4.7 Randomization

Randomization will use an adaptive biased coin algorithm using the software program R as the user interface. After CRF 4 is complete the SRC will leave the room and the second RC (referred to as RC2 from this point forward) will enter to perform the randomization process.

RC2 will enter the room with the IMPROVE research cart and open the study laptop. RC2 will open R and load the randomization algorithm program. The program will prompt RC2 to enter a) whether or not the patient takes hydroxyurea and b) how many ED visits or hospital admissions for pain the patient has had over the preceding year c) the patients unique study identification number. The randomization algorithm will then notify RC2 which treatment arm the patient has been assigned to using a letter code (treatment arm A or B). Labeled study packets will be kept in the research cart and RC2 will hand the participant an appropriately labeled packet. At this time RC2 and the participant will open the packet together to review the study materials. The steps will be as follows:

1. Inhaler training – RC2 will train the participant in proper use of the inhaled medication including inhalation technique dosing intervals, what to do about missed doses.
2. Pain diary training – RC2 will train the participant regarding proper use of the pain diaries.
3. Contact information – RC2 will instruct the participant about how to contact study personnel in the event that the participant loses medication, has questions, suffers adverse events.

Once the training is complete, the participant will be instructed to put away their medication so that other study personnel do not see it. RC2 will leave the room.

The SRC will then enter the room and explain the schedule of financial incentives. The participant will be given a \$30 gift card and a \$11 metro card. A second follow up visit will be scheduled for 8 weeks from the current date. At this point the participant will be released and any other medical care will resume.

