8.5 Adherence Status Check

CRF 8 – 8 Week Adherence Status check identifies if the participant has remained adherent to study guidelines (at least 70% of doses and 15 pain diaries). CRF 8 – 8 Week Adherence Status will be filled out by RC2 as this requires that the RC visualize study medication in an unblinded fashion. If at any time the participant falls below the cut-off for medication or diaries, they will be re-instructed to bring them back to compliance.

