13.3 Case report forms

All CRF's are maintained by the SRC with regular monitoring by the PI. Any changes to CRFs will require a modification of the IRB protocol.

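### Participants who lose an inhaler are told to contact the blinded senior coordinator, although an unblinded coordinator exists for that task: an avoidable opportunity for unblinding, cheap to close

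*Combined protocol and SAP*

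**What the plan says.** Section 5.3.4.1 states the blinding aim: "The enrollment procedure is designed to maintain blinding of the participant, the PI and the senior RC". The same section names RC2 as the one unblinded coordinator and lists among RC2's duties "refilling medication if the participant loses their medication".

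Section 4.3 describes the devices: a 60-dose Twisthaler for mometasone and a metered dose inhaler for placebo. It also denies the SRC and PI the list that decodes the packets. Under 5.3.4.7 the SRC leaves the room while RC2 dispenses and trains, and afterwards "the participant will be instructed to put away their medication so that other study personnel do not see it". Section 8.4 repeats the put-away instruction at the week 8 refill.

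Section 12.0 deals with a lost inhaler: "Participants will be given contact information for the SRC and [name] at entry into the study", and then "In the event that a participant loses their study medication they will be instructed to contact the SRC". The SRC is to direct RC2 to look up the allocation and arrange the replacement. RC2 completes CRF 11.

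On the forms, 8.5 gives CRF 8 to RC2 because "this requires that the RC visualize study medication in an unblinded fashion", and 10.3 gives RC2 CRF 9. Section 13.3 says "All CRF's are maintained by the SRC with regular monitoring by the PI", and 2.3 adds "The PI electronically signs off on all case report forms in REDCap before they are finalized". Neither section makes an exception for the forms that RC2 completes.

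**The concern.** The protocol relies on the blinded staff never learning which device a participant holds, because the devices themselves identify the arm. Its safeguards against sight are careful: no code list, the SRC out of the room, inhalers put away. Section 12.0 then makes the SRC the named contact at the moment when a participant is most likely to talk about the inhaler. RC2 is already unblinded for this purpose and carries out the replacement, and no reason is given for going through the SRC.

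At stake are the outcomes that the SRC collects in person. Sections 8.6.1 and 10.5 have the SRC administer CRF 5 at week 8 and CRF 6 at week 16, covering respiratory symptoms, health-related quality of life and adverse events. An SRC who has learned the arm could influence how these answers are elicited or recorded. Section 2.3 provides for review of the SRC's spirometry results, which suggests that the SRC also coaches that effort-dependent test. FEV1/FVC is a secondary outcome in 14.4.

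**Working it through.** The documents contain no figure on this point, so the check is a comparison of roles and of the order of events.

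1. **Who must not know the arm.** Participant, PI and SRC (5.3.4.1).

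2. **Does the device reveal the arm?** Yes, if it is described. Section 4.3 gives a different device to each arm. In Supplement 3, Module A names the Asmanex Twisthaler and describes a twist-off cap with a counter. Module B tells the participant to shake the inhaler and press it.

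3. **What happens after a loss (12.0).**
   - The participant contacts the SRC.
   - The SRC instructs RC2.
   - RC2 looks up the arm, obtains the inhaler and arranges to give it to the participant.
   - RC2 records the replacement date and the estimated doses used.

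   Only the first two steps involve the SRC, and neither needs knowledge of the arm. The exposure is the conversation itself. The safeguards in 5.3.4.7 and 8.4 cover seeing the inhaler. The supplied text contains no instruction to participants not to describe it and no script for the SRC.

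4. **Is the step through the SRC needed?** Not on the text. Section 5.3.4.1 already assigns lost-medication refills to RC2, and in 5.3.4.7 RC2 is the person who tells participants how to report a loss.

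5. **Timing.** A loss during treatment comes before at least one of the two SRC-administered questionnaires. A loss before week 8 comes before both.

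6. **Forms.** CRF 8, 9 and 11 are completed by RC2, then kept by the SRC, and monitored and signed off by the PI (13.3, 2.3). The week 8 adherence check (8.5) comes before the SRC administers CRF 5 (8.6.1). Whether the forms reveal the arm depends on their fields:
   - CRF 11, as 12.0 describes it, holds a date and an estimated number of doses, neither of which names the arm.
   - CRF 8 is described as a check against 70% of doses and 15 diaries. Both modules instruct one puff a day, so a percentage alone need not identify the arm.
   - The layouts of CRF 8 and CRF 9 are not in the supplied text. They would identify the arm only if they carried a device type or a raw counter reading that differs between devices, which is an assumption.

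7. **Which outcomes are exposed.**
   - Little affected: the medication-adherence part of the feasibility outcome, which RC2 records (8.5, 10.3), and the Aim 2 primaries eNO (an instrument reading) and sVCAM (a laboratory assay) (14.4).
   - Exposed: the questionnaire outcomes and, if the SRC performs it, spirometry.

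8. **Size.** Participants affected = number of losses × probability that the device is described to the SRC. The documents give neither factor, so no percentage of the 45 participants follows from them.

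**The case against.** The strongest reply is that 12.0 discloses nothing. The participant reports a loss, the SRC passes it on, and RC2 alone consults the code and handles the inhaler. That stands: the text shows an opportunity for a slip and no more.

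A reader might infer that each loss call unblinds one participant, 1/45 = 2.2% of the sample, and multiply up by some number of losses. The documents do not support this. They state no loss count, and the inference takes every call to include a description of the device. On the text alone the true figure could be zero.

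A reader might also infer that SRC custody of the forms unblinds every participant at week 8. That would rest on form pages that are not supplied, and the content that is described for CRF 11 and CRF 8 does not name the arm. The form route is therefore a possible risk only.

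It is also fair to say that the SRC questions participants face to face about adherence and side effects at weeks 8 and 16, with a similar chance of a slip, so rerouting loss calls does not remove every exposure. By week 16 the arm may in any case be revealed on request (10.4). The questionnaire outcomes are exploratory: 14.3 describes them as giving imprecise estimates to inform a later trial. These points lower the severity. They do not explain why 12.0 sends a loss to a blinded person when 5.3.4.1 has unblinded someone else for that task.

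**Conclusion.** The point holds as a minor inconsistency between 5.3.4.1 and 12.0. The plan unblinds RC2 to replace lost medication and then names the blinded SRC as first contact, in a trial where a description of the device gives away the arm and the SRC collects the self-reported outcomes. It is an avoidable opportunity for unblinding; no disclosure is shown. Its size cannot be stated, because the documents give no loss rate and no disclosure rate. The feasibility adherence count and eNO and sVCAM are little affected. The form-custody part is weaker: 13.3 and 2.3 make no exception for RC2's forms, which justifies a precaution, but nothing supplied shows that those forms identify the arm. A feasibility study is a good place to tidy this up before the procedure is carried into a larger trial.

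**What to change.** **Main change.** Reword 12.0 so that reports of a lost inhaler, and questions about inhaler use, go to RC2. RC2 then tells the SRC only that a replacement was issued and on what date. The contact lines in Modules A and B are redacted in the public text. They need changing only if they list the SRC for this purpose.

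**Precaution on forms.** Add an exception to 13.3 and 2.3: any field on CRF 8, 9 or 11 that identifies the device or arm is closed to the SRC and PI until data collection is complete. In the meantime those fields are checked by someone other than the SRC or PI, such as the study statistician. Naming the statistical coordinating center alone would not be enough, because 2.3 says the PI and research coordinators coordinate its data collection and analysis. If the forms hold no such field, a sentence saying so is sufficient.

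**Cost.** RC2 must be reachable by telephone. REDCap access settings need adjusting, the interim check is a small added task, and a minor amendment is required, which the DSMB would approve under 1.4.3. RC2 already carries out replacements and completes these forms, so no extra coordinator is needed.

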13.1 Data management procedures

13.2 Study logs

All study logs are maintained by the SRC with regular monitoring by the PI.

13.3 Case report forms

All CRF's are maintained by the SRC with regular monitoring by the PI. Any changes to CRFs will require a modification of the IRB protocol.

14.1 Data Analyses

14.2 Primary and Secondary Outcomes: The primary outcome for the study is feasibility. **Feasibility** will be determined by calculating the proportion of randomized patients who complete follow up and a minimum of 30 pain diaries (as was required in the PiSCES study)⁷³ with good adherence to the study medication vs. the number enrolled. Other findings relevant to feasibility will include retention rate (% who complete the study), points of attrition, recruitment rates (# approached vs. # enrolled) and adherence (via dosage counters - use of more than 70% of doses) as a function of recruitment site (clinic vs. ED).

14.3 Potential outcomes for a definitive multi-center trial. We will collect outcome data which will yield imprecise estimates of effect on patient-oriented vaso-occlusive, respiratory and safety outcomes. Vaso-occlusion will be measured in 5 ways 1) daily pain diaries (see exploration of potential definitive outcomes), 2) ED visits for pain; 3) hospital admissions (or observation unit stays) for pain 4) hospital admissions for ACS and 5) Health-related quality of life (change in ASCQ-Me score). While a primary clinical outcome was not specified, sample size calculation were based on detecting a difference in pain diary data (see data analysis). Respiratory outcomes will include self-reports of symptoms from the SAC survey. Safety outcomes include infections, adverse reactions, pain, avascular necrosis, stroke and intracranial hemorrhage. Data Collection and management for

aim 1: Data will be collected by the PI or RC in the manner described in 'subject identification and recruitment' above. All ED screening forms (CRF 1) will be kept in a file in a locked cabinet in the PI's office. Relevant laboratory data will be extracted from the medical record onto case report forms (see CRFs). Data will then be manually entered into database REDCap database.

Hardcopies will be maintained in a locked file cabinet in the PI's office. Identifiable data will be kept in either the REDCap database or on harcopy locked in a file cabinet in the PI's office. Hardcopy with identifiable data will never leave the PI's office. All data that is shared outside of the PI's office (i.e with statistician) will be stripped of identifiers and participants will be identified only by a unique ID number.

14.4 Aim 2: Primary and Secondary Outcomes: This aim will assess changes in pulmonary inflammation and vascular injury with ICS therapy. The primary outcomes for the trial will be **change in eNO (pulmonary inflammation) and sVCAM (vascular injury)** level 8 weeks after randomization. Secondary outcomes will be change in reticulocyte index, change in FEV₁/FVC ratio (expressed as percent predicted) and change in other key biomarkers.

14.5 Data Analysis: *Preliminary analyses* - Descriptive analyses for all socio-demographic and clinical variables will be performed. Preliminary data analyses will focus on examination of the distributional characteristics of measures used in the study. In this step, decisions will be made regarding possible transformations that might be required to meet the assumptions of the statistical tests that will be employed. Baseline values for individuals in each randomization assignment will be compared using t-tests, chi-square and non-parametric tests when appropriate. For outcomes that may be used in a definitive trial, univariate analyses will be performed first followed by stratified analyses with potential confounders (variables known or suspected to have associations with the frequency of painful episodes including age, gender, genotype, baseline hemoglobin, leukocyte count, and fetal hemoglobin percent). Potential confounders with p-value less than 0.2 will be included in parsimonious models.

14.6 Primary analyses: The primary outcome, **feasibility** as well as retention/recruitment rates, attrition points and adherence will be expressed for those enrolled from the ED and the hematology clinic. Feasibility measures will be compared between those enrolled in the ED vs. clinic using χ^2 statistics. Adherence (defined as use of greater than 70% of indicated doses by dosage counter) will be compared to the previously validated MARS-A score cutoff of 4.5 with a χ^2 statistic to validate the use of MARS-A in SCD.

14.7 Exploration of potential definitive outcomes: For the pain diary self-report measures of pain a linear mixed repeated measures model will be implemented with the SAS procedure MIXED to compare mometasone and placebo. The nesting variable will be participant ID number; main effects will be time, treatment group and interaction of time by treatment group. This will allow for variability in the number of diaries completed and variable effects of ICS over time (expected to increase with duration of treatment). For the measures of vaso-occlusion with poisson distributions (frequency of hospital visits for pain, ED visits for pain and hospital visits for acute chest syndrome), multivariable negative binomial regressions will be performed to estimate rate ratios based on treatment assignment. We expect self-report HRQL measures (change in ASCQ-Me score) to be approximately normally distributed. Pain diary data will be expressed in terms of several summary measures as described in the PiSCES project including number of days in 'crisis', number of pain days, number of days requiring opiate use and mean pain severity.⁷¹ Categorical summary measures will be compared with χ^2 statistic, continuous variables will be compared with t-tests or non-parametric tests as appropriate. Additionally, for potential patient-oriented outcomes, a series of Bayesian analyses will be performed. For normally distributed variables (i.e. ASCQ-Me pain domains) a posterior distribution will be estimated for the difference between treatment groups. This will be achieved by using a non-informative Gaussian distribution as the conjugate prior. Markov-chain monte carlo simulation will be used to obtain random samples from the posterior distributions of each treatment group such that the distribution of the difference between treatments can be estimated. The same procedure will be used for other patient-oriented outcomes. For poisson distributed outcomes (ED visits, hospital admissions) a gamma prior will be

used, for binomial outcomes we will use a beta prior. All Bayesian analyses will be performed in R. Bayesian analyses will also be used to estimate adverse events if any occur.

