2.2.1 IMPROVE trial organizational chart

3.0 Study overview

We will conduct a randomized, double blind, placebo-controlled, feasibility study of mometasone furoate, an inhaled cortico-steroid (ICS), for 16 weeks in individuals with SCD and recurrent cough or wheezing who do not meet clinical criteria (derived specifically for individuals with SCD) for a diagnosis of asthma. Participants will be enrolled when they are pain free and have no acute respiratory symptoms. The sample size will be 45 participants, aged ≥ 15 , with 2:1 allocation of drug to placebo. Feasibility will be determined by the proportion of individuals successfully randomized who maintain good adherence and complete at least 30 pain diaries vs. the total number enrolled.

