4.3 Study medication

As already approved by the ISMMS research pharmacy, study medication will be stored in [name] office in a locked cabinet. Thermostat will be set at all times to maintain acceptable storage temperature (59-86 °F). Throughout the week, temperature and humidity (current readings as well as min and max for both) will be logged daily on the study medication temperature log sheet (CRF13) using a Fisher Scientific digital Traceable Thermometer/Clock/Humidity monitor. Over the weekend, min and max temperature and humidity will be logged on the Monday following. Min and max temperatures are stored after the memory is cleared (once each day). [name] packages, dispenses, and maintains accountability for all study medication is assisted by the unblinded RC in packaging and distribution.

Study packets for randomization will be made from sealable envelopes. Each packet will contain sufficient medication for 8 weeks (one 60-dose mometasone twisthaler or one placebo metered dose inhaler MDI). Packets containing active medication will include 'protocol orientation module A' (a document that has training and usage instructions for the mometasone twisthaler). Packets containing placebo will contain 'protocol orientation module B' (a document that has training and usage instructions for the placebo inhaler). Each packet will also include 60 pain diaries. Packets will then be sealed and labeled with a code. The code will indicate which treatment arm the packet corresponds to. The unblinded RC will have access to a master list that reveals the coding scheme, SRC and PI will not have access to this list.

In the event that [name] is not present during study recruitment/enrollment, licensed nurse practitioner [name] will be present to oversee dispensation of study drug or placebo.

5.1 Recruitment, screening and eligibility procedures:

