- d. They answer yes to questions 12 , 14, 15 and >15 for question 13 in group 5

Investigator Approval of Eligibility: _____ Date: _____

Supplement 3: Inhaler training and adherence modules

(Affix Label Here)
 
Participant ID: _
	
Date Form Filled Out:
 
-----
 
day month year
	
Inhaled Mometasone to Promote Reduction of Vaso-occlusive Events

---	---	---

Protocol Orientation Module A

If you lose your medication

Contact study staff immediately:

[REDACTED]
[REDACTED]
[REDACTED]
[REDACTED]
[REDACTED]

Pain diaries

Pain diaries are included in your package. Try to fill out a pain diary every day. If you miss a day that's ok. You must fill out at least 30 diaries to stay in the study.

Your medicine

This package contains your medicine for this study. Take one puff of the medicine every day. The research coordinator will teach you how to use the inhaler.

(Affix Label Here) Participant ID: _____	Date Form Filled Out: - - - - - day month year	Inhaled Mometasone to Promote Reduction of Vaso-occlusive Events
--	--	--

**Protocol Orientation Module: Adapted from “BREATHE EASIER: AN
ADULT ASTHMA EDUCATION PROGRAM” and Mometasone
Package Insert**

“Breathe Easier”

Developed by the American Institutes for Research and
the Kaiser-Permanente Medical Group

National Heart, Lung, and Blood Institute

National Institutes of Health

National Asthma Education and Prevention Program

FOR ORAL INHALATION ONLY

Please read this leaflet carefully before taking this medication

This leaflet does not contain the complete information about this medication. If you have any questions about mometasone inhalation ask your health care provider or pharmacist.

IMPORTANT POINTS TO REMEMBER

- Use this medication regularly and at the same time each day, as prescribed by your health care provider. You or your child may not get the most benefit for 1 to 2 weeks or longer after starting the medication. If you or your child's symptoms do not improve in that time frame or if your condition gets worse, contact your health care provider.
- The cap is needed to use the TWISTHALER. Do not twist the mouthpiece with your hand. When the cap is removed from the TWISTHALER, the dose counter will count down by one, and show the number of doses available after this use.

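### Section 14.6 analyses counter adherence and MARS-A only as cut categories; numeric analyses should be added, with a clear power gain for the MARS-A relation but not an established one for ED versus clinic

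*Combined protocol and SAP*

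**What the plan says.** Section 14.2 lists, among the findings relevant to feasibility, "adherence (via dosage counters - use of more than 70% of doses) as a function of recruitment site (clinic vs. ED"). Section 14.6 repeats the definition: "Adherence (defined as use of greater than 70% of indicated doses by dosage counter"). It then sets two tests:

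- By site: "Feasibility measures will be compared between those enrolled in the ED vs. clinic using" a chi-square statistic.
- Against self-report: adherence "will be compared to the previously validated MARS-A score cutoff of 4.5 with a" chi-square statistic. The stated aim is to validate MARS-A in sickle cell disease.

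The underlying measure is a count. The orientation leaflet for the active inhaler (Supplement 3, Module A) says that "the dose counter will count down by one, and show the number of doses available after this use". Section 4.3 describes the two devices as "one 60-dose mometasone twisthaler or one placebo metered dose inhaler MDI". Section 3.0 gives the size of the study: "The sample size will be 45 participants".

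No section analyses percentage of doses taken, or the MARS-A score, on its numeric scale.

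**The concern.** A dose count gives each participant a percentage of indicated doses. Once it is cut at 70%, someone who took 69% is treated like someone who took none, and 71% is treated like 100%. MARS-A is cut as well, so the validation question rests on one 2x2 table from about 45 people.

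The site result also depends on where the cut sits. No rationale is given for 70%, and the change log in Supplement 1 shows that the adherence cutoff for per-protocol analyses was moved there from 80% in November 2015, after enrolment had begun.

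At stake is whether a real relation between self-reported and counted adherence could be seen with data the study intends to hold. No decision rule or power claim in the plan hangs on either comparison, so this is a modest improvement and not a threat to the main result.

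**Working it through.** **Plan's own figure.** There is none to reproduce. The power statements in 14.8 and 14.11 concern pain scores and eNO.

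**Inputs from the documents.** N = 45 (3.0); cuts at 70% of doses and MARS-A 4.5, with chi-square tests (14.6).

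**Inputs assumed because none is given.**
- Two-sided alpha 0.05 and an uncorrected Pearson chi-square.
- MARS-A: 70% of participants above the dose cut, 30–50% above the MARS-A cut, correlation 0.3 to 0.7.
- Site: ED/clinic splits of 22/23, 15/30 and 10/35; proportions adherent of 80 v 60, 70 v 50 and 80 v 50%.

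**MARS-A, approximation by hand.** Take a bivariate normal with correlation 0.4 and write p and q for the proportions above the two cuts. The correlation left in the 2x2 table is phi = (p11 − pq) / √[p(1−p)q(1−q)], and chi-square has noncentrality N·phi².

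- p = 0.7, q = 0.5: p11 = 0.4066, phi = (0.4066 − 0.35)/0.2291 = 0.247, noncentrality 45 × 0.247² = 2.75, power about 38%.
- p = 0.7, q = 0.3: p11 = 0.2561, phi = (0.2561 − 0.21)/0.21 = 0.220, noncentrality 2.17, power about 31%.
- Spearman: ρs = (6/π)·arcsin(0.4/2) = 0.385; z = atanh(0.385) × √(42/1.06) = 0.405 × 6.295 = 2.55; power Φ(2.55 − 1.96), about 72%.

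**MARS-A, simulation under the same model.**

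| Correlation | Chi-square power | Spearman power | Gap (points) |
|---|---|---|---|
| 0.3 | 19–23% | 47–48% | 24–29 |
| 0.4 | 29–40% | 73–74% | 33–45 |
| 0.7 | | | about 10–20 |
| 0.4, bimodal adherence | | | about 13–27 |

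The first two gaps are differences between the ends of the ranges. Spearman was ahead in every case run.

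**ED versus clinic, approximation by hand.** Take 80% v 60% adherent, split 22/23. The pooled proportion is (0.8 × 22 + 0.6 × 23)/45 = 0.698. The standard error is √[0.698 × 0.302 × (1/22 + 1/23)] = 0.137, so z = 0.20/0.137 = 1.46 and chi-square power is Φ(1.46 − 1.96), about 31%. On a normal scale the same difference is 0.84 − 0.25 = 0.59 SD.

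**ED versus clinic, simulation.**
- *Normal adherence.* In the case just worked, chi-square has about 30% and Wilcoxon about 45%. Over the three pairs and three splits, with either site the better one, Wilcoxon gains about 3–22 points. Adding 85 v 65 and 90 v 70 takes the gain to about 32.
- *Bimodal adherence.* Assume regular users follow Beta(18,2), mean 0.90, and near-stoppers follow Beta(2,4), mean 0.33, with the sites differing only in the mix. Chi-square against Wilcoxon:

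| Adherent | 22/23 | 15/30 | 10/35 |
|---|---|---|---|
| 80 v 60% | 29 v 21% | 24 v 18% | 17 v 14% |
| 80 v 50% | 55 v 40% | 46 v 36% | 36 v 29% |

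Here the site difference lies entirely in who crosses the cut, and the spread within each group is noise to a rank test. Over the same three pairs and splits, Wilcoxon ranges from nearly equal to about 16 points below chi-square. None of these ranges is a bound; more extreme adherence rates can go beyond them.

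**The case against.** The strongest reply is that the binaries have a purpose. Good adherence is a component of the feasibility outcome in 14.2, and 14.6 sets out to check an existing MARS-A cutoff. A correlation does not show whether 4.5 classifies people correctly. This stands, and it is why numeric analyses belong beside the chi-square comparisons and not in their place.

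A second reply is that adherence percentages are bounded and may well be bimodal, in which case the cut can be the better summary of a site difference. This also stands. A reader might infer that cutting a numeric measure must cost power in the site comparison, or that a fixed number of points is lost. The documents support neither: they give no distribution, split or adherence rate, and the sign of the difference changes between reasonable models. Nor would a numeric test rescue an underpowered comparison. At 80 v 60% adherent, Wilcoxon power is only about 45% even in the favourable model with a near-even split.

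A third reply is that the numeric data may be incomplete. A counter is described only for the active inhaler; Module B, for the placebo inhaler, mentions none. Section 12.0 has doses used before an inhaler was lost recorded as an estimate. The adherence forms (CRFs 8 and 9) are not reproduced in the text available, so what they capture cannot be checked. This is a condition on the fix. It does not favour the cut, because the 70% category needs the same count in both arms.

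Finally, 14.5 already plans to examine distributions. That is preliminary description and names no numeric analysis of adherence. Section 14.7 does compare continuous summaries of the pain diaries by t-tests or non-parametric tests, so the addition would follow the plan's own practice.

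**Conclusion.** The point holds for MARS-A. If the correlation is moderate (0.3–0.4), cutting both measures leaves chi-square with roughly half the power of Spearman or less, and the direction survived every case run, including bimodal adherence. The size depends on the assumed correlation and cut positions: the gap is about 10–20 points at correlation 0.7.

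For ED versus clinic, what holds is narrower. The planned result depends on the position of the 70% cut, and no numeric summary is planned beside it. Whether a numeric test would have more power is not established.

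This is a desirable addition to a 45-person feasibility study, with no bearing on the validity of the feasibility outcome.

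**What to change.** In 14.6:

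1. Keep the 70% binary in the feasibility composite, and keep both chi-square comparisons.
2. Add the Spearman correlation, with 95% CI, between MARS-A score and percentage of indicated doses taken, as the main measure of association. Report the 4.5 cut as classification against the 70% category.
3. Add percentage of doses by recruitment site, with the Hodges-Lehmann difference and 95% CI, as a supplement that does not depend on where the cut sits.
4. State that the dose count is recorded as a number in both arms, how it is obtained for the placebo inhaler, and how estimated doses from lost inhalers are handled.

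While the text is open, reconcile section 8.5, which counts exactly 70% as adherent, with 14.2 and 14.6, which require more than 70%.

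The cost is a few sentences and slightly more analysis, provided numeric counts exist for both inhalers.
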